#### 4.6.2 Secondary Efficacy Endpoints

The following secondary efficacy endpoints will be studied.

##### 1) Adjusted INCAT disability score

The adjusted INCAT disability score will be presented with descriptive statistics at each visit. The change from baseline in the adjusted INCAT disability score will be analysed at 24 weeks and EOS visit.

Several graphics will be produced:

- Boxplots over time of a) the at-visit values and b) change from baseline
- Waterfall plots faceted by visit of a) the at-visit values and b) change from baseline

##### 2) Time to relapse

Relapse is defined as as one of the following conditions:

- Adjusted INCAT disability score increase by 1 point compared to baseline

AND

Judging on the clinical examination and/or the neurological scales assessments, the Investigator considers change in patient's treatment is mandatory: increase in IVIg dosage, increase or initiation of a corticotherapy, immunosuppressive therapy, plasma exchange.

- Adjusted INCAT disability score increase by at least 2 points compared to baseline.

Time to relapse (measured from the first IMP infusion in I10E-1306) will be analysed using a Kaplan-Meier (KM) method. Patients without relapse will be considered censored at their last assessment of the INCAT disability score. Patients with a forbidden treatment intake before a relapse will be considered censored at the date of the first intake of a forbidden treatment.

KM estimates of the mean, the median as well as for the first and third quartile will be provided together with their associated 95% confidence interval. A KM-plot will be provided showing the incidence of relapse over time. Time of censoring will be displayed in the graph. A table will be included below the graph showing the number of patients "at risk" (i.e. without relapse), the number of patients with a relapse and the number of censored patients at the time points 0, 12, 24, 36 and 48 weeks.

Descriptive statistics will be provided for the time to relapse on the subset of patients with relapse until EOS.

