### **3.1.6. Relapsing Patients**

A relapse is defined as one of the following conditions:

- Adjusted INCAT disability score increase by 1 point compared to baseline,  
AND  
Judging on the clinical examination and/or the neurological scales assessments, the Investigator considers change in patient's treatment is mandatory: increase in IVIg dosage, increase or initiation of a corticotherapy, immunosuppressive therapy, plasma exchange.
- Adjusted INCAT disability score increase by at least 2 points compared to baseline.

Relapsing patients will undergo the study assessments scheduled at the EOS visit within 7 days and prior to the administration of any other CIDP treatment. The patient will be then withdrawn from the study and treated at the discretion of his/her physician.

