#### 3.2 HANDLING OF MISSING DATA AND OUTLIERS

Regarding the primary criterion, a patient will be also considered as a non-responder if the patient is withdrawn due to lack of efficacy of the treatment (insufficient response to the investigational medicinal product [IMP]). If the INCAT score at EOS visit is missing, then the Last Observation Carried Forward (LOCF) approach will be applied and the last available adjusted INCAT disability score will replace the missing value at EOS visit.

The LOCF approach will also be used to handle the missing data of secondary endpoints.

When AEs are documented in the diary, date-time of AE onset may be missing or incomplete. As a result, it might not be possible to determine if the AE started between the start of an infusion until 72 hours after the end of the infusion (Temporally Associated AE [TAAE]). In such cases, the response to the question "Did the

AE start within 72 hours of an infusion” will be used for determining if the AE is temporally associated to an infusion or not.

Partial dates of first symptoms and partial dates of diagnosis (collected in the I10E-1302 study) will be imputed by 15 if only the day is unknown and by 1st July if day and month are unknown. No imputation will be done if the year is unknown.

For the calculation of duration of AEs, partial start and end dates will be imputed with the first and last possible date within the period defined by the partial date, respectively. In general, no calculation of duration will be made if either the start date or stop date is missing, i.e., can't be imputed using pre-determined rules.

No other general rules for the replacement of missing data are planned.

Data listings will always show the original CRF reported values and not the imputed values.

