### 3.5 DEFINITION OF THE PROTOCOL DEVIATIONS AND POPULATIONS

#### 3.5.1 Populations

The definition of analysis sets is as follows:

- Total Treated Set (TTS): all patients who received at least one administration of the study drug.
- Full Analysis Set (FAS): all TTS patients having an available assessment of the primary efficacy criterion.
- Per Protocol Set (PPS): all FAS patients without any major deviations from protocol.

If a patient is treated with a non-permitted treatment during the study period, specifically those that confound efficacy evaluation, then all efficacy variables measured after the intake of these not-allowed treatments will be censored for the efficacy analyses. Censoring of measurements will be done up to a reasonable window from the start time of a prohibited treatment where the window is determined according to the half-life of the not- allowed treatment. The window will be adjudicated prior to database lock.

The TTS will be used for the analysis of safety data.

The FAS will be used for the primary analysis of efficacy data and the PPS to test its robustness.

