#### 4 STATISTICAL ANALYSIS

##### 4.1 DISPOSITION OF PATIENTS

In order to describe the population, descriptive statistics (number, or number and percentages) will be provided for the following:

- Patients screened (patients who signed informed consent)
- Patients enrolled
- Patients with a screening failure
- Patients who received study treatment (TTS)
  - Patients participating in the ancillary study
  - Patients who completed the study
  - Patients withdrawn early from the study and reasons for study discontinuation [AE, Protocol deviation, Withdrawal of consent, Lost to follow-up, Insufficient response to IMP, Other]  
Patients withdrawn early due to insufficient response of IMP with reason for insufficient response (INCAT, MRC sum score, R-ODS, Grip strength, CGI-Patient, CGI-Investigator, Clinical examination, Premature termination of IMP) and follow-up treatment (IVIg, Corticosteroids, Immunomodulatory or immunosuppressive agent or Other)
- Patients included in the FAS
- Patients included in the PPS

A separate in-text summary table will be produced to contain the following information: patients who received at least one dose of IMP in I10E-1302; non-responders in I10E-1302; responders in the study; and patients who discontinued. An in-text listing with all patients who were discontinued due to "Insufficient response to the IMP" may be produced. The said listing will contain identifiable relapse risk information based on review of efficacy and safety information.

Except for patients enrolled and patients with a screening failure, percentages will be calculated using the number of patients of the TTS as the denominator. For screen failure patients, a listing will be produced with the reason for screening failure and the specifications provided by the investigator. For patients who discontinued the study, a listing will be produced with the reasons of study discontinuation and the specifications provided by the investigator.

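### SAP 3.5.1 conflicts with SAP 4.6 and 4.6.2 on censoring after forbidden treatment, SAP 4.6.1 can count some changes of CIDP treatment as response, and the relapse curve can censor patients whom the responder analysis counts as failures

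*SAP*

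**What the plan says.** **Censoring.** SAP 3.5.1 applies censoring to non-permitted treatments, "specifically those that confound efficacy evaluation", and limits its length: "Censoring of measurements will be done up to a reasonable window from the start time of a prohibited treatment". The window depends on the treatment's half-life and is to be adjudicated before database lock. SAP 4.6 censors every efficacy value after any non-permitted treatment, with no window. Its list includes loop diuretics in the 24 hours before an infusion. SAP 4.6.1 then replaces a censored INCAT score with the last score before intake.

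**Time to relapse.** Relapse in SAP 4.6.2 requires a rise in adjusted INCAT: 1 point plus the investigator's judgement that treatment must change, or at least 2 points. Otherwise, "Patients without relapse will be considered censored at their last assessment of the INCAT disability score". For forbidden treatment, "Patients with a forbidden treatment intake before a relapse will be considered censored at the date of the first intake of a forbidden treatment".

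**Response.** SAP 4.6.1 requires an INCAT rise of no more than 1 and no change in CIDP treatment, which it defines by a list. SAP 3.2 adds that "a patient will be also considered as a non-responder if the patient is withdrawn due to lack of efficacy of the treatment". SAP 4.1 tabulates early withdrawals with "reason for insufficient response (INCAT, MRC sum score, R-ODS, Grip strength, CGI-Patient, CGI-Investigator, Clinical examination" among the items recorded.

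**The concern.** Two programmers, one working from SAP 3.5.1 and one from 4.6 and 4.6.2, would keep different data for the same patient. This affects the primary endpoint as well as the relapse curve. Separately, the SAP's list of treatment changes is narrower than the protocol's wording, so a patient given another active treatment could count as a success. The relapse curve and the responder rate could also disagree about a patient: relapse-free until censored in one, failed in the other.

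This matters because relapse at the lower dose is the reason SAP 4.10 gives for ending the study early. Time to relapse is also one of the few secondary endpoints still analysed rather than only listed. With so few patients, one classification is visible in the result.

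**Working it through.** The study is descriptive (SAP 3.4) and states no event or censoring count, so there is no planned figure to reproduce. The check compares the rules and then sizes the effect of one patient.

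**1. Censoring rules side by side**

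| Place | Treatments | Duration |
|---|---|---|
| Protocol 12.9.1.1 | any not allowed | all later efficacy values |
| Protocol 12.9.2.2 | any not allowed | all later adjusted INCAT scores |
| SAP 3.5.1 | those confounding efficacy | limited window, set later |
| SAP 4.6 | any on the list | all later efficacy values |
| SAP 4.6.2 | any forbidden | permanent, from first intake |

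SAP 4.6 and 4.6.2 are one rule, the second being its time-to-event form. SAP 3.5.1 differs from both in scope and duration. SAP 4.10 does not list this as a change from the protocol.

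Test case: a patient takes a listed treatment at Week 3. It is either judged non-confounding or its window has closed well before the end of study. A 2-point INCAT rise is first recorded at the Week 48 visit.
- Under 3.5.1 the Week 48 score stands. The patient fails the INCAT condition and has a relapse.
- Under 4.6 and 4.6.1 the score before intake is carried forward. If that score was unchanged from baseline, the INCAT condition is met.
- Under 4.6.2 the patient is censored at Week 3 and the relapse is not counted.

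**2. Definition of a treatment change**

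Protocol 3.2.1 requires no change at all in CIDP treatment. In SAP 4.6.1, other IVIg or plasma exchange appears only in the item that joins it to premature discontinuation for insufficient response. Take a patient who receives either one, in breach of protocol 7.2, and stays on study drug at the same dose and interval. No item on the list is met. The score before intake is carried forward, and the patient can be a responder. The same holds for an immunomodulatory agent if it is not read as an immunosuppressive drug: SAP 4.6 forbids both classes, but 4.6.1 names only the second.

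Size, with the planned range as denominator: 1/30 = 3.3 points; 1/15 = 6.7 points.

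**3. Failures that the curve can censor**

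- A patient withdrawn for insufficient response without an INCAT-defined relapse is a non-responder under SAP 3.2. The curve censors that patient at the last INCAT assessment. No protocol breach is needed.
- A patient given a CIDP-active forbidden treatment before a recorded relapse can be a non-responder under SAP 4.6.1. The curve censors that patient at intake. This needs a breach of protocol 7.2.

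Size at Week 24. Inputs: n = 15 or 30 (planned range), and d failures by Week 24 at 13% or 45%, the 24-week relapse rates that protocol 1.1.2 cites, used only as a range. Rounded, 0.13 × 15 = 1.95 gives 2; 0.45 × 15 = 6.75 gives 7; 0.13 × 30 = 3.9 gives 4; 0.45 × 30 = 13.5 gives 14.

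If everyone else is followed past Week 24, the Kaplan-Meier value is S = (n − d)/n. Censoring the j-th failure instead of counting it multiplies S by (n − j + 1)/(n − j), a rise of S/(n − j).

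| d of n | S | Rise, first failure (j = 1) | Rise, last failure (j = d) |
|---|---|---|---|
| 2 of 15 | 86.7% | 86.7/14 = 6.2 | 86.7/13 = 6.7 |
| 7 of 15 | 53.3% | 53.3/14 = 3.8 | 53.3/8 = 6.7 |
| 4 of 30 | 86.7% | 86.7/29 = 3.0 | 86.7/26 = 3.3 |
| 14 of 30 | 53.3% | 53.3/29 = 1.8 | 53.3/16 = 3.3 |

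Because the study ended early, I also let follow-up of the non-failures end evenly over Weeks 9 to 48, with failures evenly over Weeks 3 to 24 (both assumed). The rise is then 1.6 to 10.4 points. The maximum comes from 2 of 15 with one failure at Week 24, when 9 remain at risk: S = 14/15 × 8/9 = 83.0%, against 14/15 = 93.3% if that failure is censored.

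**The case against.** **The endpoints are meant to differ.** Relapse in the SAP repeats protocol 3.1.6, and a relapse curve need not equal a responder rate. The reasons listed in SAP 4.1 do not show that anyone was withdrawn without an INCAT rise: MRC, R-ODS, grip strength or CGI could support the judgement that accompanies a 1-point rise. Protocol 5.4 names relapse, not insufficient response, as a ground for stopping. These patients also stay visible in the disposition table, the listings and the censoring marks. All of this stands. It is why the relapse endpoint should be kept, and why the claim is only that the curve can censor such patients.

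**A reader might infer that ordinary relapses followed by rescue are censored.** The documents do not support that. Protocol 3.1.6 places the assessment "prior to the administration of any other CIDP treatment", so a relapse handled as planned remains an event.

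**A reader might infer three censoring rules.** There are two, because SAP 4.6 and 4.6.2 are compatible.

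**A reader might infer that all the corticosteroid wordings conflict.** They serve different purposes: a prohibition (protocol 7.2), a censoring list (SAP 4.6), an operational definition of treatment change (SAP 4.6.1), and the investigator's judgement, where "increase or initiation of a corticotherapy" carries no threshold. Only protocol 7.2 and SAP 4.6 need to match, and they do not. The protocol bars any introduction and any dose above 10 mg/day; the SAP bars an introduction only above 10 mg/day.

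**A reader might infer that loop diuretics plainly should not censor.** Protocol 7.2 deals with them by postponing the infusion. Protocol 7.1, however, lists them among drugs that could interfere with efficacy assessment. The documents leave this open.

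**On immunomodulatory agents**, SAP 4.6 treats them with immunosuppressants as one class, and a physician reviews immunosuppressive treatments before lock. That may close this part of the gap in practice. It does not close the part on other immunoglobulin and plasma exchange.

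**Conclusion.** The point holds in three parts. SAP 3.5.1 contradicts SAP 4.6, 4.6.2 and protocol 12.9.1.1 on which treatments censor efficacy data and for how long. SAP 4.6.1 is narrower than protocol 3.2.1 and can count a patient given another CIDP treatment as a responder. The relapse curve can censor patients whom SAP 3.2 or 4.6.1 counts as failures, mainly through the rule on the last INCAT assessment and, after forbidden intake, through the sentence on first intake.

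The sizes are illustrative: they rest on the planned 15 to 30 patients and on assumed failure counts and dates, and every effect is zero if no such patient exists. It would go too far to say that the reported relapse or responder results are wrong, or that the decision to stop the study is in doubt: no document gives a count of affected patients. This should be corrected before database lock, because the rules as written can give conflicting answers for the same patient. Confidence is medium.

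**What to change.** 1. **One censoring rule.** Before database lock, state the same rule in SAP 3.5.1, 4.6, 4.6.1 and 4.6.2, with the drug list and any window fixed in the SAP. Reconcile protocol 7.1, protocol 7.2 and SAP 4.6 on loop diuretics, and state whether they censor efficacy data. Record any departure from protocol 12.9.1.1 and 12.9.2.2 in SAP 4.10.
2. **Responder definition, for analysis only.** In SAP 2.5.1 and 4.6.1, count other immunoglobulin, plasma exchange and immunomodulatory agents as a change in CIDP treatment with or without discontinuation, in line with protocol 3.2.1. Record this in SAP 4.10 as made after the early assessment of results, and report the responder rate under both definitions. Reconcile the corticosteroid wording of SAP 4.6 with protocol 7.2. Add a sensitivity analysis that counts corticosteroid courses below the 4.6.1 threshold as non-response.
3. **Relapse curve.** Keep protocol-defined time to relapse as the secondary endpoint. Add a supplementary Kaplan-Meier curve, labelled post hoc, whose events are relapse, first CIDP-active forbidden treatment and withdrawal for insufficient response. Report how many patients differ between the two curves.

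Cost: SAP wording, entries in SAP 4.10, one extra curve, a second responder rate, one sensitivity analysis, and recoding of data already collected. Downside: a CIDP-active drug given for another illness counts as failure in the supplementary curve and as a treatment change under item 2. The retained definitions and the reported counts make this visible.

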##### 3) Grip strength (kPa) with the Martin vigorimeter in both hands

Grip strength (actual and normalized according to the healthy population) will be presented with descriptive statistics at baseline, week 24 and EOS for the dominant hand and the non-dominant hand side by side. The change from baseline in grip strength for the dominant hand and the non-dominant hand will be analysed at 24 weeks and at the EOS visit. The assessment at screening will be used for the determination of the dominant hand.

#### 4) Rasch-built Overall Disability Scale (R-ODS)

R-ODS will be presented with descriptive statistics at baseline, week 24 and EOS visit. The change from baseline in R-ODS will be analysed at 24 weeks and at the EOS visit.

For the endpoints 1), 3), and 4) the Hodges-Lehmann estimator and the associated 95% confidence interval will be calculated for all at-visit values as well as for the change from baseline. The change from baseline for these endpoints will be tested using a Wilcoxon signed-rank test. All statistical tests will be descriptive and will use a two-sided significance level of  $\alpha=5\%$ .

Results for response rate at 24 weeks, MRC 12 muscles sum score, Rasch-modified MRC sum score, Percentage of patients without change in CIDP treatment from baseline to 24 weeks and EOS visit, and patient and investigator CGI will be presented in listings..

## 4.7 SAFETY ANALYSES

Safety analyses will be conducted on the TTS.

### 4.7.1 Extent of Exposure

#### Patient level analyses

The extent of exposure to IMPs will be summarized on the patient level using the following variables:

- Duration of study participation (m) from signing of informed consent to EOS: (EOS visit date – date of informed consent + 1) / 30.4375
- Duration of treatment exposure (m) from the first day of IMP administration to EOS: (EOS visit date – date of first IMP infusion + 1) / 30.4375
- Average course frequency:

$\frac{1}{n_c} \sum_{j=1}^{n_c} (\text{start date of course}_{j+1} - \text{start date of course}_j)$ , with  $n_c$  the number of courses of the patient

For the last course, the date of the EOS visit will be used as the *start date of course*  $n_c+1$ .

- Total number of courses
- Average number of infusions per course:  $\frac{1}{n_c} \sum_{j=1}^{n_c} (\text{number of infusions at course } j)$
- Total number of infusions  $\sum_{j=1}^{n_c} (\text{number of infusions at course } j)$
- Cumulative dose over all infusions (g and g/kg):  $\sum_{j=1}^{n_c} \sum_{k=1}^{n_{I_j}} (\text{dose at infusion } k \text{ of course } j)$ , with  $n_{I_j}$  the number of infusions at course  $j$  of the patient

- Average dose per course (g and g/kg):  $\frac{1}{n_c} \sum_{j=1}^{n_c} \sum_{k=1}^{n_{Ij}}$  (dose at infusion  $k$  of course  $j$ )
- Maximum dose over all infusions (g and g/kg)
- Maximum flow rate over all infusions (mL/kg/h)

#### Course level analyses

The extent of exposure to IMPs will be summarized on the course level using the following variables:

- Total number of infusions
- Course dose (g and g/kg)
- Average dose per infusion (g and g/kg):  $\frac{1}{n_I} \sum_{k=1}^{n_I}$  (dose at infusion  $k$ ), with  $n_I$  the number of infusions of the course
- Initial flow rate of the first course infusion (mL/kg/h)
- Duration of initial flow rate of the first course infusion (min)
- Maximum flow rate over all infusions (mL/kg/h)
- Duration of the course (day)

#### Infusion level analyses

The extent of exposure to IMPs will be summarized on the infusion level using the following variables:

- Dose (g and g/kg)
- Initial flow rate (mL/kg/h)
- Maximum flow rate (mL/kg/h)
- Number of flow rate changes
- Duration of the infusion (min)

In all three analysis levels, dose (g and g/kg) will be derived based on the prescribed administered volume reported in the CRF:

- Dose (g) = Daily volume administered (mL) \* batch concentration (i.e. 0.1 g/L)
- Dose (g/kg) = Daily volume administered (mL) \* batch concentration (i.e. 0.1 g/L) / body weight (kg) at the start of the course

A listing will be provided with the presented variables of each analysis level (patient, course, infusion).

#### 4.7.2 Adverse Events

All AEs occurring during the study will be classified by preferred term (PT) and system organ class (SOC) using the version 17.1 of the Medical Dictionary for Regulatory Activities (MedDRA).

- Seriousness *Serious* if one of the follow-ups is serious / *Non-serious* otherwise

- Seriousness criterion For each of the criteria listed below: *Yes* if at least one of the follow-ups had *Yes* for the corresponding criterion / *No* otherwise
  - *Results in death*
  - *Life-threatening*
  - *In patient hospitalisation or prolongation of existing hospitalisation*
  - *Persistent or significant disability / incapacity*
  - *Congenital anomaly / birth defect*
  - *Important medical event*
- Start date time Start date time of the first follow-up
- End date time End date time of the last follow-up
- Ongoing *Yes* if last sequence follow-up is ongoing / *No* otherwise
- Did the AE start within 72h after an infusion? *Yes* if the first follow-up started within the first 72h after an infusion / *No* otherwise
- Intensity maximum(Intensity of follow-ups)  
Increasing order of importance: *Mild / Moderate / Severe*
- Action taken maximum(Action taken of follow-ups)  
Increasing order of importance: *None / Dose changed / Interruption of IMP / Discontinuation of IMP*
- Corrective medication *Yes* if at least one of the follow-ups had a corrective medication / *No* otherwise
- Relationship to study drug *Yes* if at least one of the follow-ups had a relationship to study drug assessed as *Yes* / *No* otherwise
- Outcome maximum(Outcome of corresponding follow-ups)  
Increasing order of importance: *Unknown / Recovered without sequela / Recovered with sequelae / Recovering / Not recovered / Fatal*

AEs will be classified as I10E-1302 AEs or treatment emergent AEs (TEAEs) according to the date of onset:

- I10E-1302 AEs are defined as events with a date-time of onset before the start date-time of the first infusion in I10E-1306.
- TEAEs are defined as events with a date-time of onset on or after the start date-time of the first infusion in I10E-1306.

Treatment Emergent Adverse Events (TEAE)

The following rules for the derivation of the TEAE status will be used in the order of display.

1. If the date-time of the AE onset is known: TEAE = “Yes” if AE onset date-time  $\geq$  start date-time of first IMP infusion / “No” otherwise.
2. If the date-time of the AE onset is not known but the complete date of the AE onset is known:
  - TEAE = “Yes” if AE onset date  $>$  start date of first IMP infusion.
  - TEAE = “Yes” if AE onset date = start date of first IMP infusion and investigator’s assessment of the time of onset  $\neq$  “Before infusion”.
  - TEAE = “No” otherwise.
3. If the date of AE onset is a partial date and the investigator’s assessment of the time of onset is not missing: TEAE = “Yes” if investigator’s assessment of the time of onset “During infusion”, “ $\leq 72h$ ” or “ $> 72h$ ”.
4. If the date of AE onset is a partial date and the investigator’s assessment of the time of onset is missing:
  - TEAE = “Yes” if last possible date in the period defined by the partial date  $\geq$  start date of first IMP infusion / “No” if the last possible date in the period defined by the partial date  $<$  start date of first IMP infusion.
5. TEAE = “Yes” otherwise.

A summary of the total number of AEs, and number and percentage of patients with at least one AE will be presented. This summary will include:

- All TEAEs
- TEAEs by seriousness criterion
- TEAEs by drug relationship
- TEAEs by temporal association with infusion (TEAE within the 72h after an infusion Yes/No)
- TEAEs by severity (Mild / Moderate / Severe)
- TEAEs by Action taken with IMP (None / Dose reduced / Dose increased / Discontinuation of IMP / Interruption of IMP)
- TEAEs by outcome (Resolved without sequelae / Resolved with sequelae / Not recovered / Recovering / Fatal / Unknown)

A similar summary table will be produced for TAAEs as well as drug related TEAEs.

All TEAEs, SAEs and drug-related AEs will be summarized by SOC and PT, showing number of TEAEs, and number and percentage of patients with at least one TEAE, sorted by decreasing incidence of SOC and PT within SOC. Summary of TEAEs will also be presented by relevant subgroups (e.g., by age group [using

median as cut point], sex, race [white and non-white]/ethnicity [Hispanic or Latino and not Hispanic or Latino], and BMI [using median as cut point]). The rate of TEAEs by course and by infusion will be calculated as the absolute number of TEAEs divided by the number of courses and number of infusions, respectively and will be presented in the same manner.

Duration of TEAEs will be calculated as AE end date – AE start date + 1 and presented with descriptive statistics on recovered AEs (i.e. AEs with an outcome of "Recovered without sequelae" or "Recovered with sequelae"). Statistical unit of analysis will be the individual recovered TEAE. No imputation will be performed for the purposes of computing duration.

The time between the last administration of IMP to the onset of the TEAE will be calculated as AE start date – Date of previous IMP infusion and will be presented with descriptive statistics using the individual TEAE as statistical unit.

All SAEs, drug related AEs, AEs leading to dose changes or discontinuation of IMP, and other significant AEs will be listed.

Time of onset since last administration for most common TEAEs (those which occurred in at least 10% of the patients) will be presented by patient status (naïve/pre-treated) and by course number. Summary statistics including 95% confidence intervals will be calculated for each TEAE preferred term.

I10E-1302 AEs will be listed by patient.

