### **Follow-up of Adverse Events:**

All AEs or SAEs assessed as not related to study medication, including clinically significant laboratory tests or physical examination findings, must be followed until the event resolves, the condition stabilizes, the event is otherwise explained, or the final study visit occurs, whichever comes first.

AEs or SAEs assessed as related to study drug will be followed for as long as necessary to adequately evaluate the subject's safety, or until the event stabilizes, or the subject is lost to follow up. If resolved, a resolution date should be provided.

The Investigator is responsible for ensuring that follow-up includes any supplemental investigations indicated to elucidate the nature and/or causality of the AE. This may include additional clinical laboratory testing or investigations, histopathological examinations, or consultation with other health care professionals as is practical.

If a patient is withdrawn from study due to safety reasons, he/she should be followed until the event disappears, is otherwise explained or the patient's condition has stabilised.

Any patient who voluntarily withdraws from the study should be carefully questioned for the possible occurrence of an adverse event. Whenever possible, a patient should be followed through the last scheduled visit.

If no follow-up information can be provided after all efforts and attempts, the Investigator must document the outcome as “unknown” and provide a justification.

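### AE outcome is taken as the worst status ever recorded, so an event that later resolves can be tabulated as unresolved and lost from the duration summary

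*SAP*

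**What the plan says.** SAP 4.7.2 describes how several follow-up records of one adverse event are collapsed into a single analysis record. For outcome the rule is "Outcome maximum(Outcome of corresponding follow-ups)", and the increasing order is "Unknown / Recovered without sequela / Recovered with sequelae / Recovering / Not recovered / Fatal".

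Two related items in the same list use the final record instead. The end date is the "End date time of the last follow-up", and an event is ongoing "if last sequence follow-up is ongoing".

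The derived outcome is used in two places in SAP 4.7.2:

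- The summary table has rows for "TEAEs by outcome (Resolved without sequelae / Resolved with sequelae / Not recovered / Recovering / Fatal / Unknown)". Similar tables are produced for TAAEs and for drug-related TEAEs.
- Duration is "presented with descriptive statistics on recovered AEs", meaning events whose outcome is one of the two recovered states.

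Protocol 12.10.1 plans TEAE duration as a safety analysis. For drug-related events, Protocol 9.5.3 adds: "If resolved, a resolution date should be provided". Nothing in either document replaces the maximum with the final status.

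**The concern.** A maximum suits intensity or seriousness, where the peak is the quantity wanted. Outcome describes where the event stands at the end of follow-up. Once an interim *Recovering* or *Not recovered* has been stored, the maximum can never return to a recovered state, whatever happens later.

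Three things follow:

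- The analysis record can contradict itself, with an end date and ongoing set to No beside an outcome of *Not recovered*.
- The outcome tables overstate unresolved events. The rule does not always err on the cautious side, however: *Recovering* followed by *Recovered with sequelae* is reported as *Recovering*, so the sequelae do not appear in the outcome row.
- Resolved events with an interim unresolved record drop out of the duration summary. Longer events have more opportunity to acquire such a record, so the events lost are plausibly the longer ones.

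Safety is the only secondary objective (Protocol 2.2, SAP 2.1.2). The study expected 15 to 30 patients (Protocol 12.3) and was stopped early (SAP 4.10), so a few misclassified events could visibly move these descriptive figures.

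**Working it through.** The plan gives no figure to reproduce. The check applies the stated rule to possible record sequences and then works out the effect on mean duration under stated assumptions.

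**Inputs.** The rank order, the end-date and ongoing rules, and the restriction of duration to recovered outcomes all come from SAP 4.7.2. *Resolved* in the summary table is read as *Recovered* in the derivation. *Corresponding follow-ups* is read as all records of the same event.

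**Step 1: two-record sequences starting in an unresolved state.** Two first outcomes times six second outcomes gives 2 × 6 = 12 sequences.

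- In 5 the maximum equals the last outcome: *Recovering* then *Recovering*, *Not recovered* or *Fatal*; *Not recovered* then *Not recovered* or *Fatal*.
- In 2 the last outcome is *Unknown*, and the maximum keeps the earlier known status.
- In 5 the maximum reports a superseded status:

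| First record | Last record | SAP outcome | Resolved, but excluded from duration |
|---|---|---|---|
| Recovering | Recovered without sequelae | Recovering | Yes |
| Recovering | Recovered with sequelae | Recovering | Yes |
| Not recovered | Recovered without sequelae | Not recovered | Yes |
| Not recovered | Recovered with sequelae | Not recovered | Yes |
| Not recovered | Recovering | Not recovered | Not resolved |

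Check: 5 + 2 + 5 = 12.

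**Step 2: non-fatal sequences ending in recovery.**

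- Two records: 5 × 2 = 10 sequences. The rule keeps those whose first outcome is *Unknown* or recovered, 3 × 2 = 6, and excludes 4.
- Three records: 5 × 5 × 2 = 50 sequences. It keeps 3 × 3 × 2 = 18 and excludes 32.

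These counts show which sequences are affected, not how often they occur. Events with one record, and events whose last outcome is no better than any earlier one, are unaffected. *Recovered with sequelae* followed by *Recovered without sequelae* keeps the earlier label but stays in the duration summary.

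**Step 3: effect on mean duration.** Let *p* be the share of resolved TEAEs that are dropped and *r* their mean duration relative to the rest. Both are assumed, since the documents give neither. If the retained events have mean *D*, the mean over all resolved events is *D*(1 − *p* + *pr*), while the reported mean is *D*. The relative shortfall is

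1 − 1/(1 − *p* + *pr*).

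For *p* = 5% and *r* = 2: 1 − 1/1.05 = 4.8%. For *p* = 20% and *r* = 3: 1 − 1/1.40 = 28.6%.

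| *p* | *r* = 0.5 | *r* = 1 | *r* = 2 | *r* = 3 |
|---|---|---|---|---|
| 5% | −2.6% | 0% | 4.8% | 9.1% |
| 10% | −5.3% | 0% | 9.1% | 16.7% |
| 20% | −11.1% | 0% | 16.7% | 28.6% |

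A negative value means the reported mean is too long.

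**The case against.** **Frequency.** The effect needs at least two stored records, with an unresolved status followed by improvement, and nothing shows how often outcome is completed at each follow-up. Visits are three weeks apart, and the diary collects start and end times for review at the next visit, so a short infusion-related event may be over when first entered. This stands: the number affected is unknown, and the 5% to 20% and the duration ratios have no source in the documents. It does not remove the defect, because SAP 4.7.2 is itself written for events with a first and a last follow-up.

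**Worst case is a deliberate choice.** Most items in the list use worst-case or any-Yes rules, and overstating unresolved events is conservative. That is fair for the outcome rows as far as it goes. It does not justify removing resolved events from the duration summary.

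**Sequelae remain visible elsewhere.** Sequelae that meet the disability criterion stay in the seriousness summary. Serious events, drug-related events and events leading to dose change or discontinuation are listed individually. This is largely right: the loss is in the outcome row, although non-serious, unrelated events lack that listing safeguard.

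**A last-known-outcome rule also carries status forward.** When the final record is *Unknown*, outcome would come from an earlier record while end date and ongoing come from the last. Protocol 9.5.3 says that if no follow-up information can be obtained "the Investigator must document the outcome as" unknown. That governs what the investigator records, not which status the analysis keeps. The point stands as a limit on the remedy, but the SAP rule also ranks *Unknown* lowest and so has the same feature.

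**Conclusion.** The rule is wrong as written. Any event whose earlier *Recovering* or *Not recovered* status later improves is reported with the superseded status. If it has resolved, it is also lost from the duration summary. This follows from the text of SAP 4.7.2 and needs no assumption beyond reading the follow-ups as all records of the same event.

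The size in this study cannot be stated. The duration percentages are illustrative, and their sign depends on whether the dropped events are longer or shorter than the rest. The impact is confined to the outcome rows of the TEAE, TAAE and drug-related TEAE summaries and to the duration summary. AE counts, seriousness, severity, relatedness, TAAE status and the primary endpoint do not change. It should be corrected, because the present rule misreports resolved events and the correction is almost free.

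**What to change.** Replace the outcome rule in SAP 4.7.2 with:

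> Outcome = last known (non-missing, not Unknown) outcome across the follow-ups of the event; Fatal if any follow-up is Fatal; Unknown only if no follow-up has a known outcome.

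Select events for the duration summary on this outcome. Outcome then agrees with the last-follow-up rules for end date and ongoing status, except when the final record is *Unknown*. In that case the earlier known status is kept, and the end date and ongoing flag still come from the final record. An event with no usable end date still has no computable duration.

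The cost is one line in the SAP and one line of code. No new data are needed.
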